8.2 Recording of Adverse Effects

At each contact with the subject, the investigator will seek information on adverse effects of the fiber supplementation by specific questioning and, as appropriate, by examination. Information on all adverse effects will be recorded immediately in the source document, and also in the case report form (CRF). All clearly related signs, symptoms, and abnormal diagnostic procedures results should be recorded in the source document, though should be grouped under one diagnosis.

The clinical course of each event will be followed until resolution, stabilization, or until it has been determined that the study treatment or participation is not the cause. Serious adverse events that are still ongoing at the end of the study period will be followed up to determine the final outcome. Any serious adverse device effects that occur after the study period will be recorded and reported promptly (see section 8.3 below).

The minimum initial information that will be captured in the subject's source document concerning the adverse event includes:

CONFIDENTIAL

This material is the property of the University of Chicago.
Do not disclose or use except as authorized in writing by the study PI

05.16.2023

- Study identifier
- Subject number
- A description of the event
- Date of onset
- Investigator assessment of the association between the event and study treatment
- Current status
- Whether study treatment was discontinued
- Whether the event is serious and reason for classification as serious

8.3 Reporting of Adverse Events and Unanticipated Problems

Researchers will submit reports of the following problems within 10 working days from the time the investigator becomes aware of the event:

Any adverse event that occurs any time during or after the research study, which in the opinion of the principal investigator is:

- **Unexpected** (An event is “unexpected” when its specificity and severity are not accurately reflected in the protocol-related documents, such as the IRB-approved research protocol, any applicable investigator brochure, and the current IRB-approved informed consent document and other relevant sources of information, such as product labeling and package inserts.)

AND

- **Related** to the research procedures (An event is “related to the research procedures” if in the opinion of the principal investigator or sponsor, the event was more likely than not to be caused by the research procedures.)

The above will be completed regardless of whether the event is serious or non-serious, on-site or off-site

Protocol Deviations

Any protocol deviations initiated without the The University of Chicago IRB approval that may affect the scientific soundness of the study, or affect the rights, safety, or welfare of study subjects, will be reported to the IRB as soon as a possible, but no later than 5 working days of the protocol deviation.

8.4 Medical Monitoring

The Principal Investigator will oversee the safety of the study at the site. This safety monitoring will include careful assessment and appropriate reporting of adverse events.

8.4.1 Data Monitoring Board

A Data Safety Monitoring Board (DSMB) will monitor the safety of the study. The DSMB will continually review safety data and halt the study for any substantial imbalance in adverse events. Full details are provided in the DSMB charter.

8.4.2 Overall Stopping Rules

This study will be suspended at any time if a study related death occurs in a subject on active therapy or upon the hospitalization of the second of two study related hospitalizations. If the study is suspended, screening, enrollment and POIT increases will immediately stop but active subjects will continue on current dosing unless otherwise directed by the FDA. The study and POIT dose escalation will not resume until discussed with the DSMB and FDA.

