Exclusion criteria	
 • History of a chronic disease (other than asthma, allergic rhinitis, and atopic dermatitis) that is at significant risk of becoming unstable or requiring a change in chronic therapeutic regimen • History of mast cell disease • History of recurrent idiopathic or virally induced urticaria, angioedema or anaphylaxis • Any history or presence of autoimmune, cardiovascular disease, chronic lung disease (other than asthma), malignancy, psychiatric illness, or gastrointestinal inflammatory conditions, including celiac disease, inflammatory bowel disease, eosinophilic esophagitis or other eosinophilic gastrointestinal disease • Current participation in any other interventional study • Subject who has undergone any type of oral immunotherapy • Severe asthma or uncontrolled mild to moderate asthma • Uncontrolled atopic dermatitis • Current use of oral steroid medications • Use of >1 bursts of oral steroid medications in the past year • Inability to eat by mouth the fiber supplementation or placebo control and peanut flour for any reason • Use of any therapeutic antibody (biologic medication) or any immunomodulatory medication in the past 12 month (other than a short course of oral steroids) • Current use of any type of immunotherapy • Pregnancy or lactation • Allergy to potato, corn, oat or cow's milk • Unwillingness to carry an epinephrine autoinjector • Unwillingness to comply with activity restrictions during OIT or any other study procedure
Study Product and Planned Use	A prebiotic, resistant potato starch (RPS), will be given as a dietary supplement before and during oral immunotherapy to peanut
Reference therapy	Oral immunotherapy to peanut
Treatment Description	Subjects who meet inclusion criteria will be randomized 1:1 to receive either RPS or placebo. After 30 days of prebiotic therapy, subjects will start peanut oral immunotherapy (POIT) in addition to the prebiotic and continue through a prescribed course of POIT, approximately 180 days. After completion of POIT up dosing, subjects will continue on maintenance POIT plus prebiotic therapy for an additional 180 days at which time they will undergo a DBPCFC. Subjects will then stop prebiotic therapy and continue on maintenance POIT in extended observation for approximately 4 years.

CONFIDENTIAL

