3.1 General Design

This study is a randomized, double-blind, placebo controlled, single center clinical trial. Subjects are anticipated to be in this study for 1 year with extended, active monitoring for an additional 4 years. After enrollment, screening and randomization, patients will be assigned to consume either RPS or placebo for

CONFIDENTIAL

This material is the property of the University of Chicago.
Do not disclose or use except as authorized in writing by the study PI

05.16.2023

30 days. At the end of the 30 days, patients will begin the standard of care treatment for peanut allergy, peanut oral immunotherapy. Initial dose escalation and up-dosing of POIT plus prebiotic will take approximately 180 days to complete. At the end of the maintenance phase, subjects will undergo a DBPCFC to determine efficacy of treatment. Finally, patients will be monitored for approximately 4 year following completion of the active drug dosing (off prebiotic) therapy during the continued immunomodulation/extended maintenance phase of POIT.

Description of DBPCFC

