6.2 Visits 2 and 3 (within 4 weeks of visit 1)

- Stool sample collection (visit 2 only)
- Vital signs
- Physical examination, including height and weight
- Spirometry (if has asthma diagnosis; as COVID allows)
- DBPCFC
- Randomization
- Prebiotic dispense

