6.3 Visit 4 (30 days after visit 3)

- Interval medical history
- Vital signs
- Physical examination, including height and weight
- Spirometry (if has asthma diagnosis as COVID allows)
- Skin prick testing
- Blood draw
- Stool sample collection
- Collection of dose and symptom logs
- Standard of care consent for POIT
- POIT initial dose escalation day

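### The automatic death rule in section 8.4.2 does not cover a single study-related death at the screening peanut challenge, because no therapy has started by then

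*Combined protocol and SAP*

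**What the plan says.** Section 8.4.2 (Overall Stopping Rules) has two triggers for suspending the whole study. The first is a death: "This study will be suspended at any time if a study related death occurs in a subject on active therapy". The second is a count of hospital admissions: the study is suspended "upon the hospitalization of the second of two study related hospitalizations". On suspension, "screening, enrollment and POIT increases will immediately stop but active subjects will continue on current dosing", and "The study and POIT dose escalation will not resume until discussed with the DSMB and FDA". The protocol does not define active therapy.

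The order of events is set elsewhere. Section 3.1 says: "After enrollment, screening and randomization, patients will be assigned to consume either RPS or placebo". Section 6.2, for visits 2 and 3, lists the food challenge, then randomization, then "Prebiotic dispense". The Treatment Description in the Study Summary says: "After 30 days of prebiotic therapy, subjects will start peanut oral immunotherapy (POIT) in addition to the prebiotic". Section 6.3 accordingly places the "POIT initial dose escalation day" at visit 4, 30 days after visit 3.

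**The concern.** A suspension is meant to protect children in screening as well as those on treatment, since screening heads the list of activities it stops. Yet the death trigger applies only to children already on therapy. The screening challenge gives peanut to allergic children who have had no desensitization. Section 1.5 says reactions are expected at these challenges and that the most serious can threaten life. If a child died there from the challenge, section 8.4.2 read literally would let the next child be challenged without a mandatory pause. At stake is whether a halt in that case is required by rule or left to judgement. The trial's results are not at stake.

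**Working it through.** **Step 1: has any therapy begun at the screening challenge?** The undefined term could mean three things. I check each against the visit order.

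| Reading of active therapy | When it starts | Started at the screening challenge? |
|---|---|---|
| Resistant potato starch only | Dispensed at visit 3, after the challenge | No |
| Either starch, active or placebo | Dispensed at visit 3, after the challenge | No |
| POIT | Visit 4, 30 days after visit 3 | No |

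The schedule puts the second challenge day and randomization at the same visit, so their order within visit 3 matters. Section 4.1 makes a dose-limiting reaction at or below 100 mg on the screening challenge an inclusion criterion, and the Treatment Description randomizes only children who meet the criteria. The challenge must therefore be complete before randomization and dispensing, which is also the order in section 6.2.

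**Step 2: apply section 8.4.2 to one study-related death at that challenge, with no earlier study-related hospitalization.**
- Death trigger: not met under any of the three readings.
- Hospitalization trigger: at most 1 of the 2 admissions required, so not met.
- Result: no automatic suspension.

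**Step 3: does another provision require a halt?**
- Section 8.4.1: the one halt criterion stated for the DSMB is a marked imbalance in adverse events. A child who dies before randomization belongs to no arm.
- Section 8.3: reporting of unexpected, related events within 10 working days. It suspends nothing.
- Section 8.4.2, second trigger: it could apply if the death involved an admission and another study-related admission had already occurred, but not to a single event.
- Section 8.4.3: concerns individual subjects only.
- Section 8.4: safety oversight by the principal investigator, which is discretionary.

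**Step 4: how likely is the event?** The plan gives no figure to reproduce. The only documented input is 30 randomized children. Two inputs are assumptions: *f*, the share of challenged children who are not randomized (0 to 0.5), and *p*, the risk of death per peanut challenge (1 in 1,000,000 to 1 in 10,000).

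Number of uncovered peanut challenges: *n* = 30/(1 − *f*). With *f* = 0, *n* = 30; with *f* = 0.25, *n* = 40; with *f* = 0.5, *n* = 60.

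Chance of at least one death: 1 − (1 − *p*)^*n*.

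| *p* | *n* | Chance |
|---|---|---|
| 1 in 1,000,000 | 30 | 0.00003, or 0.003% |
| 1 in 100,000 | 40 | 0.0004, or 0.04% |
| 1 in 10,000 | 60 | 0.0060, or 0.6% |

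The last row pairs the worst value of each assumption and is an upper bound under them, not an expected value.

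**The case against.** The strongest reply is that the narrow scope may be intended. Section 8.4.2 can be read as a treatment-safety rule, since it also freezes POIT increases and addresses continued dosing. Section 1.5 calls the screening challenge standard of care, with no more than minimal added risk over an open clinical challenge. A sponsor could reasonably tie the automatic pause to therapy and leave a death at a diagnostic challenge to the DSMB. This is arguable, but it sits badly with a suspension that stops screening. The challenge is also a scheduled study procedure that decides eligibility.

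The second reply is that a halt would happen anyway. The DSMB has a general mandate to monitor safety and reviews the data continually. The protocol does not say that imbalance is its only ground for stopping, and section 8.4.1 refers to a charter for full details. This stands. A reader might infer that the trial has no means of stopping after a screening death. The documents do not support that: they show only that section 8.4.2 does not compel it, and the charter may do so.

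A reader might also picture children being given rising doses until they react. That is not the design. Section 3.1 ends screening doses at 100 mg whether or not the child reacts, and keeps the 300, 600 and 1000 mg doses for the exit challenge. A challenge stops at any moderate or severe symptom, or at two mild ones. There is continuous monitoring, with epinephrine in the room and a resuscitation team in the hospital.

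Nor do the documents show that the higher-dose exit challenge is outside the rule. At that point subjects are on maintenance POIT with the supplement or placebo.

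**Conclusion.** The point holds as a gap in the wording of one safety rule. Read literally, section 8.4.2 does not suspend the study for a single study-related death at the screening challenge. This follows from the visit order and does not depend on how active therapy is defined.

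Its practical weight is small. Under the stated assumptions the chance of the event is about 0.003% to 0.6%, and a discretionary halt is probable. I am confident about the wording of section 8.4.2. I make no claim about the trial's full set of stopping provisions, because the charter has not been seen. This is a minor correction to consider.

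**What to change.** In section 8.4.2, replace the active-therapy qualifier on the death trigger with: *in any subject after consent, whether or not randomized or on therapy, including during a DBPCFC*. The words on randomization are needed because the child in question belongs to no arm. Keep the study-related condition, so that attribution is still judged, and leave the hospitalization trigger, the list of paused activities and the conditions for resuming as they are. Then check that the DSMB charter carries the same trigger.

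The wording would also settle whether placebo subjects count, and would cover subjects who have stopped treatment but are still followed under section 8.4.3. The sponsor should confirm that this wider reach is wanted.

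The cost is one amended phrase and one check of the charter. The downside is that a death before therapy would also pause POIT increases in treated children until the discussion with the DSMB and FDA, even though neither POIT nor fiber was involved. Those children would stay on their current dose meanwhile, unless the FDA directed otherwise, so the burden is a delay in updosing. That seems a fair price for a mandatory review after a child's death in a study procedure.

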8.4.3 Individual Stopping Rules

Individuals may stop participation at any time for any reason, including inability to tolerate study related side effects. If individuals discontinue either study drug treatment or POIT treatment at their discretion or because they meet an individual stopping rule, they will continue to be monitored for the length of

CONFIDENTIAL

This material is the property of the University of Chicago.
Do not disclose or use except as authorized in writing by the study PI

05.16.2023

the study unless the subject withdraws consent. Subjects will not undergo a DBPCFC at exit unless the subject reaches POIT maintenance dosing of 300mg peanut protein for 6 months.

Specific individual stopping rules are as follows:

1. A subject misses 5 or more consecutive days of POIT or study drug dosing due to non-compliance (but not illness)
2. The subject misses 14 consecutive days of POIT or study drug dosing for any reason
3. Administration of three or more doses of epinephrine as a result of an allergic reaction caused by a single POIT dose
4. Meeting any exclusion criteria during the course of the study
5. Development of eosinophilic esophagitis (biopsy proven)
6. Any reason at the discretion of the investigator that continued participation in this study places the subject at unacceptable risk or for any reason prevents safe conduct of the study.

In this study, if a subject fails to tolerate an updose after 3 or more attempts but do not meet the aforementioned stopping criteria, the subject will continue maintenance dosing at the last tolerated dose indefinitely. Failure to tolerate an updose after 3 or more attempts is not an individual stopping rule for purposes of this study.

9 Data Handling and Record Keeping

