1.5 Risks/Benefits

Risks Associated with RPS and placebo (corn starch)

RPS is a food product and generally regarded as safe (GRAS) by the following. Under sections 201(S) and 409 of the Federal Food, Drug, and Cosmetic Act, “any substance that is intentionally added to food is a food additive, that is subject to premarket review and approval by FDA, unless the substance is generally recognized, among qualified experts, as having been adequately shown to be safe under the conditions of its intended use, or unless the use of the substance is otherwise excepted from the definition of food additive. Under sections 201(s) and 409 and FDA’s implementing regulations in 21 CFR 170.3 and 21 CFR 170.30, the use of a food substance may be GRAS either through scientific procedures or, for a substance used in food before 1958, through experience based on common use in food. Under 21 CFR 170.30(b), general recognition of safety through scientific procedures requires the same quantity and quality of scientific evidence as is required to obtain approval of the substance as a food additive. General recognition of safety through scientific procedures is based upon the application of generally available and accepted scientific data, information, or methods, which ordinarily are published, as well as the application of scientific principles, and may be corroborated, by the application of unpublished scientific data, information, or methods.” GRAS notice 310 claims exemption from the requirement of premarket approval for potato fiber and was closed on 12-24-2009 with no questions from the FDA. In addition, under 21 CFR 170.30(c) and 170.3(f), general recognition of safety through experience based on common use in foods requires a substantial history of consumption for food use by a significant number of consumers. Potatoes have been commonly consumed throughout history by numerous populations.

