In this study, we are enrolling subjects between the ages of 4 and 17, inclusive with peanut allergy and asking them to consume either a RPS or a control starch (corn starch). This consumption of either product may increase the overall caloric intake of subjects which may lead to weight gain. Subjects in the RPS group will be asked to consume 1 tablespoon (12 grams) of a fiber supplement daily which contains 40 calories/tablespoon. Subjects in the control group will be asked to consume 1 tablespoon (8 grams) of ACS daily which contains 30 calories/tablespoon. In addition, an increase in fiber consumption may lead to bloating, gas and/or constipation.

Risks Associated with DBPCFC

In this study DBPCFCs will be conducted in accordance with the recommended PRACTALL guidelines. The screening DBPCFC is utilized as the standard of care to confirm peanut allergy and does not confer higher than minimal risk than a open label food challenge used clinically to confirm peanut allergy prior to POIT. The screening DBPCFC will also establish a threshold for reactivity for comparison with the exit DBPCFC. The exit DBPCFC will be used to establish efficacy of POIT and confirm safety of accidental ingestion of peanut. The exit DBPCFC also does not confer more than minimal risk above a standard of care open label food challenge used during POIT to confirm tolerance of peanut ingestion. DBPCFC are expected to induce allergic reactions. Reactions range from mild (nausea, few hives) to severe (wheezing, diffuse urticaria, rhinitis/conjunctivitis, vomiting/diarrhea, impending doom) to potentially life threatening (low blood pressure, difficulty breathing, neurologic changes). Administered in a controlled setting under the supervision of experienced staff, food challenges are considered safe and are the

CONFIDENTIAL

current gold standard for the diagnosis of peanut allergy. As soon as symptoms consistent with an allergic reaction are witnessed, interventions to stop the reaction are begun (H1 antihistamines and epinephrine).

Risks Associated with POIT

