Anthony's Organic Peanut Flour will be utilized for POIT, and doses will be prepared by the study PI or by trained study staff under direct supervision of the PI. Peanut flour will be mixed into water to form a slurry and delivered via a medication syringe to optimize at home dosing until doses are sufficiently high to be measured with standard kitchen utensils (i.e. 1/8 teaspoon). Throughout the course of POIT, patients will be instructed to eat a large meal before every dose and will also be instructed to abstain for any activity that will increase his/her heartrate for 3 hours following each dose, including physical activity (other than light walking) and hot showers. No sleep will be allowed during this observation period. Patients will be asked to avoid use of nonsteroidal anti-inflammatory medications throughout the course of oral immunotherapy (acetaminophen will be allowed). No updosing will occur in menstruating women during menses. If a patient develops a fever ($T > 100^{\circ}\text{F}$), asthma flare, or gastrointestinal illness during the course of POIT, dosing will be held for up to two days and restarted upon fever resolution at home. If a fever lasts longer than two days, patients will return to clinic to restart. If more than 2 consecutive days of doses (but less than 7 days) are missed at any time during POIT for any reason (including fever), patients will be restarted at 50% of their current dose under supervision of the investigator but allowed to return to current dosing at home at the discretion of the investigator in 2-4 days. If 7 or more consecutive days of doses are missed, POIT will be restarted under supervision of the investigator at less than 50% of the current dose with a modified updosing schedule.

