For initial dose escalation, patients will be instructed to eat a large meal prior to arrival in clinic then eat snacks throughout the morning. Patients will be admitted to the University of Chicago special procedure unit for initial dose escalation where walls are transparent glass for continuous observation by trained nursing staff. Patients will be monitored on a continuous heart rate and oxygen saturation monitor throughout the procedure. Intramuscular epinephrine and oral antihistamines will be in the room with the patient prior to initiation of any doses. The patient's temperature and blood pressure will be checked before each dose. A resuscitation cart will be available within the area. Patients will be dosed every 20 to 30 minutes. Doses given on initial dose escalation day are as follows: 0.5mg, 1mg, 1.5mg, 3mg, 6mg of peanut protein. If patients tolerate at least 3mg on initial dose escalation, they will return the following day for their first monitored dose of 3mg. If the patient tolerates, the 3mg they will continue this dose daily for two weeks then return for updosing. The updosing schedule will be as follows: 3mg, 6mg, 12mg, 20mg, 40mg, 80mg, 100mg, 125 mg, 150 mg, 250 mg, 300 mg. If the patient is experiencing gastrointestinal side effects that do not subside prior to updosing in 2 weeks, updosing may be delayed from 1 week to indefinitely until side effects improve and at the discretion of the investigator. If POIT is discontinued for any reason, patients will continue to be observed on study but not undergo the final DBPCFC (unless the patient withdraws from the study). Patients will continue on 300mg dosing until the end of study at which time they may choose to consent to an extended maintenance study or follow up with their allergist for continued standard of care monitoring and dosing.

CONFIDENTIAL

SCHEDULE OF PROCEDURES									
Phase of Study	SCREENING			INITIAL ESCALATION		UPDOSING	MAINTENANCE	EXIT DBPCFC	
Visit Number	V1	V2	V3	V4	V5	V6 - V14	V15	V16	V17
Visit Day/Month	(D-65)	(D-37)	(D-30)	D1	D2	D16 - M8	M11	M14	M14
Time Window		Within 4 weeks of V1	Within 1 Week of V2	30 Days After V3	1 Day After V4	Every 2-4 weeks	3 months post V14	3 months after V15	Within 1 Week of V16
Informed Consent/Assent	X								
Medical/Allergy History	X								
Interval Medical History				X		X	X	X	
Concomitant Medications	X	X	X	X	X	X	X	X	X
Vital Signs	X	X	X	X	X	X	X	X	X
Physical Exam	X	X	X	X	X	X	X	X	X
QoL Assessment	X								

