5.2 Treatment Regimen

Subjects will be asked to take 1 tablespoon of fiber supplement (or placebo daily) mixed with a liquid or semi-solid food, such as pudding, applesauce or guacamole. If the supplementation causes abdominal distress, the participants will be asked to cut the dose in half for one week then increase back to the full tablespoon dose.

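### Missed starch alone is an individual stopping event under 8.4.3, with no stated route back, so a 5-day lapse can end the supplement under test

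*Combined protocol and SAP*

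**What the plan says.** Section 8.4.3 of the protocol lists six individual stopping rules. Rule 1 reads "A subject misses 5 or more consecutive days of POIT or study drug dosing due to non-compliance (but not illness"; rule 2 reads "The subject misses 14 consecutive days of POIT or study drug dosing for any reason". The sentence on consequences opens "If individuals discontinue either study drug treatment or POIT treatment at their discretion or because they meet an individual stopping rule" and goes on to say only that such children stay under monitoring for the study's length unless consent is withdrawn. The same section makes the exit double-blind placebo-controlled food challenge (DBPCFC) depend on six months at 300 mg of POIT and sets no condition on starch.

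Section 3.1 adds: "If POIT is discontinued for any reason, patients will continue to be observed on study but not undergo the final DBPCFC". It also gives restart steps for missed peanut doses, the longest of which begins "If 7 or more consecutive days of doses are missed, POIT will be restarted under supervision of the investigator".

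For starch, 5.2 has a single adjustment: "If the supplementation causes abdominal distress, the participants will be asked to cut the dose in half for one week", after which the full tablespoon returns. It is tied to symptoms, not to missed days. On risk, 1.5 states "RPS is a food product and generally regarded as safe (GRAS" and warns that "an increase in fiber consumption may lead to bloating, gas and/or constipation".

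The Study Summary plans starch for 30 days before POIT, about 180 days of up-dosing and 180 days of maintenance. Section 5.3 provides a paper diary and weighing of returned product to track compliance.

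**The concern.** The trial asks whether resistant potato starch (RPS), taken before and throughout POIT, improves POIT. A rule that takes a child off starch after a short lapse cuts exposure to the intervention being tested. That child's later stool samples and exit challenge then describe someone no longer on the assigned supplement.

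The rule does not say which product stops or for how long, so two investigators could handle the same lapse differently. The gap matters even before POIT begins. For the first 30 days starch is the only product, so a child can meet rule 1 in the lead-in, and the protocol does not say whether that child goes on to initial escalation at visit 4.

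**Working it through.** **Step 1: can missed starch alone trigger a stop?** Section 8.4.3 names study drug treatment and POIT treatment as separate things, so study drug there means the starch (RPS or corn-starch placebo). Rules 1 and 2 join the two with 'or'. Missed starch alone is therefore enough. Rule 1 exempts illness; rule 2 does not.

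**Step 2: what follows?**
- *Starch stops, POIT continues.* This fits best: 8.4.3 treats the two products as separately discontinuable and ties the exit DBPCFC to POIT only.
- *POIT stops as well.* Nothing says so, but nothing rules it out. If it happened, 3.1 would remove the exit DBPCFC.
- *The child leaves the study.* Section 4.4.1 allows withdrawal for failing protocol requirements, so this too is open.

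**Step 3: can starch resume?** The restart steps in 3.1 cover peanut only. The half-dose week in 5.2 covers abdominal distress only. No other section provides a return after missed starch. That the stop is permanent is an inference from this silence and from the word 'discontinue'.

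**Step 4: scale.** The plan gives no figure of its own to reproduce. Inputs: planned starch T = 30 + 180 + 180 = 390 days (Study Summary); lapse length L = 5 or 14 (rules 1 and 2); e = the day on which the lapse ends. Days taken before the lapse are e − L, so under a lasting stop:

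days lost = T − (e − L)

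Day 30 is the end of the lead-in and day 210 the end of up-dosing; day 360 is 30 days before the planned end.

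| L | e | Taken before lapse | Lost, lasting stop | Lost, resumed |
|---|---|---|---|---|
| 5 | 30 | 25 | 365 (93.6%) | 5 (1.3%) |
| 5 | 210 | 205 | 185 (47.4%) | 5 (1.3%) |
| 5 | 360 | 355 | 35 (9.0%) | 5 (1.3%) |
| 14 | 30 | 16 | 374 (95.9%) | 14 (3.6%) |
| 14 | 210 | 196 | 194 (49.7%) | 14 (3.6%) |
| 14 | 360 | 346 | 44 (11.3%) | 14 (3.6%) |

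**Step 5: sensitivity to the planned duration.** The schedule of procedures runs from D-30 to month 14, or about 30 + 14 × 30.4 = 456 days (assuming 30.4 days a month). For L = 5 the losses become 456 − 25 = 431, 456 − 205 = 251 and 456 − 355 = 101 days. The contrast with 5 days remains.

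**Step 6: effect on an arm.** With 15 children per arm (30 randomized 1:1), planned exposure is 15 × 390 = 5,850 child-days. One affected RPS child removes 365/5,850 = 6.2%, 185/5,850 = 3.2% or 35/5,850 = 0.6%, against 5/5,850 = 0.09% if starch resumes. The number of such children cannot be derived from the documents.

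**The case against.** **Lost outcomes.** A reader might infer that each such child loses the primary outcome, 1 of 15 in an arm. The documents do not support that. It requires missed starch to end POIT or participation, which no section says. The 8.4.3 condition for the exit DBPCFC concerns POIT alone, and POIT is described in 3.1 as standard-of-care treatment, with its own consent at visit 4 (6.3). Even a child without an exit DBPCFC need not drop out of the endpoint, because the plan does not say whether such a child is excluded or counted as a failure. This objection stands.

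**Average loss.** One might also say that a lapse costs about half the planned exposure on average. That follows from assuming a permanent stop at an evenly spread time; any such stop would lose about half. It is not evidence about this trial, so only the dated examples are used here.

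**A stopping rule may serve adherence, not safety.** True, and a threshold for non-adherence is a design choice. But ending the supplement does not repair adherence; it turns a short gap into a long one. If investigators are expected simply to resume starch, the starch trigger does nothing and should go.

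**Peanut needs a supervised restart and a food does not.** This is fair: the absence of a starch restart procedure is unsurprising in itself. The difficulty is that a stopping rule applies to starch with no statement that it can be taken up again.

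**A smaller repair would do.** One sentence saying that a starch trigger stops starch only would settle the ambiguity, but without resumption it would leave the loss of exposure in place.

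**Conclusion.** The point holds in a limited form. As written, 5 or more consecutive days of missed starch through non-compliance, or 14 for any reason, is a stopping event even when POIT is going to plan. The likeliest consequence is that starch ends while POIT, monitoring and the exit DBPCFC continue. No return to starch is provided, and no safety reason is given for stopping a GRAS food because days were missed.

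The size is per child: 365, 185 or 35 days lost instead of 5, out of about 390. It assumes that the stop is lasting, which the text implies but does not state.

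How many children this touches, and the direction and size of any effect on the primary endpoint, are unknown. The rule is the same in both arms and no bias between arms is shown. The change is worth making because it costs little and protects the exposure the trial was set up to test.

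**What to change.** Limit rules 1 and 2 in 8.4.3 to POIT doses, leave rules 3 to 6 unchanged, and add to 5.2:

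> After a gap in the supplement the child resumes the assigned supplement (with the existing half-dose week if abdominal distress occurs), and the gap dates are recorded from the diary. A supplement gap alone, including one in the 30-day lead-in, is not a reason for withdrawal under 4.4.1, does not end or prevent POIT, and does not cancel the exit DBPCFC.

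Children may still stop the supplement by choice, and rule 6 still lets the investigator act on individual risk.

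The cost is an amendment of a few words in 8.4.3 and two sentences in 5.2. It is identical in both arms, so the blind is unaffected, and the diary is already in use. If children are already enrolled, apply it to all ongoing children from the amendment date, and list with dates any child already stopped for missed starch, by arm once unblinded. The downside is that restarting may bring brief gas or bloating that has to be told apart from POIT side effects.

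How rules 1 and 2 fit with the POIT restart steps in 3.1 is a separate question that this change does not settle.
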